5.6 Arithmetic Calculations

Change from Baseline

The arithmetic difference between a post-baseline value and the baseline value:

Change (absolute) from Baseline = (post-baseline value – baseline value)

Change (percent) from Baseline = [(post-baseline value – baseline value) / baseline value] x 100

Body Mass Index (BMI)

Body Mass Index will be calculated using the following formula:

BMI (kg/m^2) = weight $(kg) / [height (cm)/100]^2$

Subject Incidence for AEs

The subject incidence for a given event in a given time period is defined as the number of subjects with at least 1 reported occurrence of the event divided by the number of subjects who are at risk for having the event at the beginning of the given time period. For subjects with multiple occurrences of the same event, the event will only be counted once per subject.

6. Analysis Sets

6.1 Full Analysis Set

The full analysis set (FAS) is defined according to intent-to-treat analysis to include all subjects enrolled into the study

6.2 Safety Analysis Set

The safety analysis set (SAS) includes all subjects in the FAS who received as least one (1) dose of investigational product.

6.3 PK Analysis Set

The PK analysis set will consist of all subjects for whom at least one (1) PK parameter or endpoint can be adequately estimated.

6.4 Bone Turnover Marker Analysis Subset (PD Analysis Set)

The bone turnover marker analysis set will consist of all subjects for whom at least a baseline BTM measurement of interest and at least 1 post-baseline BTM measurement of interest.

6.5 Bone Mineral Density (BMD) Analysis Set

The bone mineral density (BMD) analysis set includes subjects in the FAS who have a baseline lumbar spine DXA BMD measurement and at least 1 post-baseline lumbar spine DXA BMD measurement.

7. Planned Analyses

7.1 Interim Analysis and Early Stopping Guidelines

No interim analysis is planned; however, Amgen, in consultation with the investigators, will review all available accumulating data before making dose escalation recommendations. Once the data becomes available, dose-aggregate and per subject PK data will also be reviewed, but it will be ensured that results do not reveal individual treatment assignments.

7.2 Primary Analysis

Please refer to Section 7.3.

7.3 Final Analysis

The final analysis will occur after all subjects have completed the study. The objective of the final analysis is to evaluate the safety and PK data and the final analysis will be performed at the end of the trial. All data will be cleaned and a database lock will occur.

8. Data Screening and Acceptance

8.1 General Principles

The objective of the data screening is to assess the quantity, quality, and statistical characteristics of the data relative to the requirements of the planned analyses.

8.2 Data Handling and Electronic Transfer of Data

The Amgen Global Study Operations-Data Management (GSO-DM) department will provide all data to be used in the planned analyses. This study will use the RAVE database.

8.3 Handling of Missing and Incomplete Data

The following imputation for missing or incomplete data will be performed if required: Non-pharmacokinetic measurements (e.g., biomarker data) that are below the lower limit of quantification will be considered equal to half of the lower limit of quantification for all analyses unless specified otherwise.

Serum PK concentrations below the lower limit of quantifications will be set to zero for the estimation of the PK parameters for each subject and for the calculation of the

summary statistic for each time point. However, missing PK concentrations will not be imputed.

No imputation will be done on incomplete stop date of an AE or a concomitant medication.

Missing and incomplete start dates of an adverse event or concomitant medication taken will be imputed as outlined in Appendix B.

8.4 Detection of Bias

Lack of protocol compliance and the potential for biased statistical analyses will be examined by assessing the incidence of important protocol deviations in each cohort. Other factors that may bias the results of the study include

- Important protocol deviations likely to impact the tolerability, safety analysis and interpretation of the endpoints as well
- Detection of adverse events and/or serious adverse events likely to impact the safety analysis
- The timing of and reasons for early withdrawal from treatment and from study

8.5 Outliers

Pharmacokinetic (PK) serum concentration data will be evaluated for outliers by visual inspection and decisions to re-assay individual samples will be made in accordance with standard pharmacokinetic evaluation practice. Histograms will be examined to identify outliers in any of the continuous variables used in the analyses. Unexpected and/or unexplained values in categorical data will be identified by utilizing frequency tables. Outliers due to data entry errors will be corrected by the study team before final database lock. The validity of any questionable values or outliers will be confirmed. Outliers or any questionable values with confirmed validity will be included in the analyses. All confirmed outlier data will be included in the analyses presented in this statistical analysis plan unless there is sufficient scientific justification (e.g., important protocol deviation leading to invalid data) to exclude them.

8.6 Distributional Characteristics

Where appropriate, the assumptions underlying the proposed statistical methodologies will be assessed. If required data transformations will be utilized.

8.7 Validation of Statistical Analyses

Programs will be developed and maintained, and output will be verified in accordance with current risk-based quality control procedures.

Tables, figures, and listings will be produced with validated standard macro programs where standard macros can produce the specified outputs.

The production environment for statistical analyses consists of Amgen-supported versions of statistical analysis software; for example, the SAS System version 9.4 or later.

9. Statistical Methods of Analysis

9.1 General Considerations

Descriptive statistics will be provided for selected subject disposition, demographics, safety, PK, and PD end points. Descriptive statistics on continuous measurements will include means, medians, standard deviations, quartiles (Q1, Q3) and minimum and maximum, while categorical data will be summarized using frequency counts and percentages. Data will be presented and summarized by cohort and visit as appropriate. Graphical summaries of the data may also be presented. When data are summarized by visit, the values recorded against the scheduled visits listed in the protocol will be used. When assessing minimum/maximum increases or decreases over the study, all assessments, including unscheduled assessments will be used. In general, data listings will be sorted by, dose, subject and visit unless specified otherwise.

9.2 Subject Accountability

The disposition of all subjects will be tabulated by cohort. The subjects who received investigational product, completed investigational product, discontinued investigational product and reasons for discontinuing, completed study and discontinued study and reasons for discontinuing will be summarized in number and percentage.

Key study dates for the first subject enrolled, last subject enrolled, last subject end of investigational product and the last subject end of study will be presented.

9.3 Important Protocol Deviations

Important Protocol Deviations (IPDs) categories are defined by the study team before the first subject's initial visit and updated during the IPD reviews throughout the study prior to database lock. These definitions of IPD categories, subcategory codes, and descriptions will be used during the course of the study. Eligibility deviations are defined in the protocol.

9.4 Demographic and Baseline Characteristics

Demographic (ie, collected age (years), sex, race, ethnicity (Hispanic, non-Hispanic), body composition (height [cm], weight [kg], BMI [kg/m²])) and baseline disease

characteristics (ie, lumbar spine BMD, bone mineral content (BMC), bone area, and BMD Z-score, bone turnover markers (sCTX, P1NP), laboratory parameters (calcium corrected by albumin, phosphorus, creatinine, serum 25-OH vitamin D, eGFR), iPTH, fracture history (Any historical fracture (Yes, No), **nonvertebral fracture**), baseline use of vitamin D, baseline use of calcium, prior osteoporosis medication use (Yes, No), type of OI (I, II, III, and IV) will be summarized by cohort using descriptive statistics based on the Full Analysis Set defined in Section **6.1**.

Historical nonvertebral fractures are as reported on fracture history eCRF, excluding skull, facial, mandible, cervical vertebrae, thoracic vertebrae, lumbar vertebrae, metacarpus, finger phalanges, and toe phalanges and fractures associated with high trauma or pathologic fractures.

9.5 PK and Efficacy Analyses

9.5.1 Analyses of Primary Endpoint(s)

Serum romosozumab concentrations will be determined using a validated assay. Individual serum concentration-nialtime plots for romosozumab will be presented for each subject as well as mean concentration-time plots for each dose cohort. PK parameters will be estimated using non-compartmental methods. Actual dosing and sampling times will be used for calculation of PK parameters. Summary statistics will be generated for each PK parameter for each dose cohort. The PK analysis set will be used to for these analyses.

9.5.2 Analyses of Secondary Efficacy Endpoint(s)

Actual value and percent change from baseline in BMD, BMC and bone area at the AP lumbar spine will be descriptively summarized at each visit for each dose cohort. The change from baseline in BMD Z-score at lumbar spine will be checked against weighted estimated mean (SE) of 0.01 (0.09) (95%CI: -017, 0.18) based on meta-analysis from historical controls (Letocha et al, 2005; Rauch et al, 2009; Ward et al, 2011). Graphs showing summary statistics (actual value and change from baseline) of BMD Z-score, and percent change from baseline of BMD at lumbar spine over time by visit for age groups will be provided. The results from the historical controls will contextualize the observed BMD results at the dose level review meeting. The BMD analysis set will be used to for these analyses.

9.6 Safety Analyses

9.6.1 Adverse Event

The Medical Dictionary for Regulatory Activities (MedDRA) version 25.0 or later will be used to code all events categorized as adverse events to a system organ class and a preferred term.

The subject incidence of adverse events will be summarized for all treatmentemergent adverse events, serious adverse events, adverse events leading to withdrawal of

investigational product, fatal adverse events, and adverse events of interest. The severity grade of all treatment-emergent

adverse events will be summarized based on Severity Intensity Scale for Adverse Events.

Subject incidence of all treatment-emergent adverse events, serious adverse events, adverse events leading to withdrawal of investigational product, and fatal adverse events will be tabulated by system organ class and preferred term in descending order of frequency. Subject listing of all treatment-emergent adverse events will also be provided.

Subject incidence of events of interest (EOI; standardized MedDRA queries and/or Amgen customized queries) will also be summarized according to their categories and preferred term. Events of interest of hypersensitivity and malignancy will be identified using a narrow search/scope in standardized MedDRA queries (SMQ). Event of interest of hypocalcemia, injection site reaction, hyperostosis and osteoarthritis will be identified using Amgen-defined MedDRA search strategies. **Serious cardiovascular adverse events will be identified using cardiac and vascular system organ class (SOC) in MedDRA.** Adjudicated-positive adverse events of osteonecrosis of the jaw (ONJ) will also be summarized as EOIs.

The number and percentage of subjects reporting adverse events will be evaluated for each dose cohort, across dose cohorts, and will also be tabulated by relationship to study drug. In addition, summary of cranial nerve examination at each visit and the result change from entry exam over time for each cohort will be tabulated.

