6. TREATMENT PROCEDURES

6.1 Classification of Product

The Amgen investigational products used in this study is romosozumab

The other protocol-required products used in this study include: calcium and vitamin D.

The Investigational Product Instruction Manual (IPIM), a document external to this protocol, contains detailed information regarding the storage, preparation, destruction, and administration of romosozumab.

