6.3 Other Protocol-required Therapies

All other protocol-required supplements, including calcium and vitamin D, that are commercially available are not provided or reimbursed by Amgen (except if required by local regulation). The investigator will be responsible for obtaining supplies of these drugs.

All subjects are required to take daily supplements of 30-50 mg/kg (not to exceed 1000 mg calcium) and at least 800 IU vitamin D for the duration of the study to minimize the risk of hypocalcemia.

If a subject becomes hypercalcemic over the course of the study, the calcium and/or vitamin D supplementation may be discontinued until serum calcium concentrations has returned to the normal range.

If a subject becomes hypocalcemic over the course of the study, the calcium and/or vitamin D supplementation may be increased, per medical judgment of the investigator.

In instances where a subject is experiencing tolerability issues with daily elemental calcium, the subject should be instructed to try different calcium salt formulations. If this strategy fails, the investigator may document that only a lower calcium supplementation dose is tolerated by the subject or that dietary supplementation is required and this will be allowed. Tolerability issues for vitamin D should be managed using the same approach as outlined for calcium above.

The dose, start date, stop date, and frequency for calcium and vitamin D are to be recorded on the eCRF. The reason for dose change of calcium and/or vitamin D supplementation is to be recorded on the eCRF.

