8.3.2 Reasons for Removal From Study

Reasons for removal of a subject from the study are:

- decision by sponsor
- withdrawal of consent from study
- death
- lost to follow-up

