9. SAFETY DATA COLLECTION, RECORDING, AND REPORTING

9.1 Definition of Safety Events

9.1.1 Adverse Events

An adverse event is defined as any untoward medical occurrence in a clinical trial subject. The event does not necessarily have a causal relationship with study treatment. The investigator is responsible for ensuring that any adverse events observed by the investigator or reported by the subject after signing of the ICF through day 169/EOS visit, End of Treatment visit, or 30 days after the last dose of IP (whichever period is longer) are reported using the Events eCRF.

The definition of adverse events includes worsening of a pre-existing medical condition. Worsening indicates that the pre-existing medical condition or underlying disease (eg, diabetes, migraine headaches, and gout) has increased in severity, frequency, and/or duration more than would be expected and/or has an association with a significantly worse outcome than expected. A pre-existing condition that has not worsened more than anticipated (ie, more than usual fluctuation of disease) during the study, or involves an intervention such as elective cosmetic surgery or a medical

procedure while on study, is not considered an adverse event. Change in severity from previously reported grade to another distinct grade (in the opinion of the investigator) should be recorded on the Event eCRF. The investigator's clinical judgment is used to determine whether a subject is to be removed from treatment due to an adverse event. In the event a subject, or subject's legally acceptable representative requests to withdraw from protocol-required therapies or the study due to an adverse event, refer to Section 8.1 for additional instructions on the procedures recommended for safe withdrawal from protocol-required therapies or the study.

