10.4.3.7 Adverse Events

Subject incidence of all treatment-emergent adverse events will be tabulated by system organ class and preferred term according to the medical dictionary for regulatory activities (MedDRA) terminology. Tables of fatal adverse events, serious adverse events, adverse events leading to withdrawal from IP or other protocol-required therapies and adverse events of interest (eg, hypocalcemia, adverse events potentially related to hypersensitivity, malignancy, injection site reactions, hyperostosis, osteoarthritis, and serious cardiovascular events) will also be provided. The number and percentage of subjects reporting adverse events will be evaluated for each dose cohort, across dose cohorts, and will also be tabulated by relationship to study drug. Adverse events resulting in treatment discontinuation will be identified.

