9.6.8 Exposure to Investigational Product

Subject listing of manufacturing lot numbers and a separate listing of unique manufacturing lot numbers used in this study will be provided. Details for each romosuzomab administration will be listed for every subject.

Descriptive statistics will be produced to describe the exposure to IP by cohort.

10. Changes From Protocol-specified Analyses

According to Section 10.4.3.6 in protocol version superseding amendment 3 dated 28 February 2023, shifts in laboratory parameters between baseline and the most extreme post baseline values will be assessed base on the Severity Intensity Scale for Adverse Events. However, the laboratory abnormality with clinical significance is considered as adverse event. Therefore, the grade shifts in laboratory parameters will not be conducted.

11. Literature Citations / References

12. Appendices

Appendix A. Technical Detail and Supplemental Information Regarding Statistical Procedures and Programs

For the baseline assessment (excluding DXA), regardless of the width of the visit window, if there are multiple records within a Baseline window, the record that is the closest to and on or prior to Study Day 1 will be considered as the baseline value.

For the post-baseline assessment, if more than 1 visit falls within the defined window, the result from the visit closest to the target day will be used. If 2 evaluations are of the same distance from the target day, the result from the later visit will be used. If more than one evaluation on the same date, the average of the results will be used. Only laboratory results collected from the central laboratory will be averaged in the case of duplicate results.

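### SAP 9.6.1 narrows the protocol's adverse-event withdrawal table to investigational product without declaring it, and no specified output identifies a non-fatal adverse-event-driven study exit after the last dose

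*SAP*

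**What the plan says.** Protocol 10.4.3.7 lists the adverse-event tables to be produced. One of them is a table of "adverse events leading to withdrawal from IP or other protocol-required therapies". Protocol 6.1 defines the second group: "The other protocol-required products used in this study include: calcium and vitamin D". Protocol 6.3 requires these supplements of all subjects, including "at least 800 IU vitamin D for the duration of the study to minimize the risk of hypocalcemia". For a subject who becomes hypercalcemic, it adds that "the calcium and/or vitamin D supplementation may be discontinued until serum calcium concentrations has returned to the normal range".

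SAP 9.6.1 refers to IP only, in both places where it describes the output: the overall incidence summary and the table by system organ class and preferred term ("adverse events leading to withdrawal of investigational product, and fatal adverse events will be tabulated"). SAP Section 10, which is reserved for changes from protocol-specified analyses, has one entry, on laboratory severity shifts. It ends "Therefore, the grade shifts in laboratory parameters will not be conducted".

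On leaving the study, protocol 9.1.1 provides for a subject or representative who "requests to withdraw from protocol-required therapies or the study due to an adverse event". Protocol 8.3.2 begins "Reasons for removal of a subject from the study are" and gives four reasons: sponsor decision, withdrawal of consent, death and loss to follow-up. SAP 9.2 summarizes study discontinuations with their reasons, by cohort.

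**The concern.** Section 1 of the SAP says that it details the analyses outlined in the protocol of 28 February 2023, and Section 10 declares a single departure. A reader will therefore take the rest as conforming. On this table it does not conform, and nothing shows whether the narrowing was a decision or an oversight.

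Safety and tolerability is a secondary objective, and the stated hypothesis is that romosozumab will be safe and well tolerated. Stopping a required therapy, or leaving the study, because of an adverse event is a direct sign of tolerability. The supplements are part of the regimen under study, given to limit the risk of hypocalcemia. With the SAP as written, the withdrawal table could be empty although a child had stopped calcium or vitamin D because of an adverse event. The disposition table could likewise show an early exit without linking it to the event that prompted it.

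**Working it through.** The plan has no figure to reproduce here: the study is descriptive and the sample size rests on practical considerations. The check sets the provisions side by side.

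**1. Scope of the withdrawal table**

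| Source | IP | Calcium, vitamin D |
|---|---|---|
| Protocol 10.4.3.7 | yes | yes |
| SAP 9.6.1, overall summary | yes | no |
| SAP 9.6.1, table by organ class and term | yes | no |
| SAP Section 10, declared change | none | none |

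**2. Could the omitted category contain events?** Yes. The supplements run for the whole study, so exposure continues after the last IP dose. Protocol 6.3 foresees stopping them for hypercalcemia. Protocol 6.4 foresees withholding or permanently discontinuing other protocol-required therapies, as appropriate, for potential hepatotoxicity. Protocol 8.1 lets a subject decline them and stay on study. Protocol 9.2.1 classes a laboratory change that requires an adjustment in current therapy as an adverse event, so stopping a supplement for hypercalcemia is tied to a reportable event.

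**3. Do other SAP outputs supply the classification?**
- Treatment-emergent events run from first dose to end of study (SAP 5.1). They are tabulated, summarized by severity and listed by subject (SAP 9.6.1). The event is therefore counted.
- Hypercalcemia is not among the named events of interest; hypocalcemia is.
- Relationship is tabulated for study drug only, although protocol 9.2.1 also collects relatedness to the other required therapies.
- SAP 9.2 gives disposition for IP and for the study, not for the supplements.

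None of these is specified to show that an event led to stopping calcium or vitamin D.

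**4. Non-fatal study exit because of an adverse event**
- Before the last dose, such an exit also ends IP, so the IP-withdrawal table can hold it.
- After the last dose there is no IP left to withdraw, so that table cannot hold it.
- The four reasons in protocol 8.3.2 include no adverse-event category, so a disposition table built on them would not label it.
- A fatal exit is covered by the fatal-event table and by death as a reason.

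**5. Scale.** One unclassified subject is 1/4 = 25% of a cohort, 1/16 = 6.3% of the minimum enrollment and 1/24 = 4.2% of the maximum. These figures show the weight of one case, not how many to expect.

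**The case against.** The strongest reply is that nothing disappears. Every treatment-emergent event to end of study is counted, graded and listed, and serum calcium is summarized at each visit. In a study of 16 to 24 subjects a reader can inspect the listing. This stands. It rules out an inference that a reader might draw from the mismatch, namely that tolerability is understated. The incidence figures are unaffected; only a label is missing.

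The supplement example can also be questioned. Protocol 6.3 describes stopping until calcium normalizes, which may be an interruption, and the protocol does not say whether an interruption counts as withdrawal. That is fair, and the SAP needs to settle it. It does not make the category empty, since protocol 6.4 and 8.1 cover other ways of stopping.

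The hypothesis concerns romosozumab, not calcium or vitamin D. That would be a reason to change the protocol's table openly, in SAP Section 10, but not to leave the change undeclared.

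The study-exit gap is not a departure from the protocol, which never asked for a table of adverse events leading to study discontinuation. Protocol 9.1.1 is conditional, and 8.1 urges keeping subjects on study where safe and feasible. The End of Study form is not in the documents and may hold finer reasons than 8.3.2. All of this stands, so this part is a suggested addition only.

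A reader might also take the share of study time after the last dose as the size of the gap. The documents do not support that: dosing days are blacked out, and elapsed time does not measure missed events.

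**Conclusion.** The protocol-SAP mismatch is established by the text alone. A protocol-specified output has been narrowed in SAP 9.6.1, and Section 10 does not say so. The consequence is loss of classification: an adverse event that led to stopping calcium or vitamin D would be reported as an event but not as one leading to withdrawal of a required therapy. No number of affected subjects can be derived, because neither document gives adverse-event or withdrawal rates.

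The second part is weaker. No specified output identifies a non-fatal adverse-event-driven exit after the last dose, provided that the end-of-study data follow the four reasons in protocol 8.3.2. If the case report form records an adverse-event reason, the SAP 9.2 summary may already show it.

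**What to change.** In SAP 9.6.1, restore the other protocol-required therapies to the withdrawal summary and table, and state whether a temporary interruption of calcium or vitamin D counts as withdrawal. If the narrower table is intended, declare and justify it in Section 10 instead.

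As a cheap addition, list adverse events associated with early discontinuation from the study.

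The sources are already collected: action taken for each event (protocol 9.2.1), the reason for any calcium or vitamin D dose change (protocol 6.3), and the end-of-study data. Confirm first that the action-taken field can be tied to the supplements, because protocol 9.2.1 does not say which product it refers to. If it cannot, use the recorded reason for the supplement change.

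The cost is SAP wording and one or two small tables or listings.

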2.3 Pediatric Risk Assessment

Romosozumab has demonstrated a favorable benefit-risk in postmenopausal women at high risk for fracture. The safety profile was evaluated in more than 14,000 subjects with the most common adverse reactions (\geq 1/10) being viral upper respiratory tract infection and arthralgia. Key safety risks for romosozumab include serious cardiovascular events of myocardial infarction and stroke, hypersensitivity reactions, hypocalcemia, and rare cases of osteonecrosis of the jaw (ONJ) and atypical femoral fracture (AFF). More detailed information about the known and expected benefits and risks may be found in the Romosozumab Investigator's Brochure.

Overall, pediatric subjects treated with romosozumab in this study are expected to have a risk profile comparable to that observed in adults. The potential risk of serious

cardiovascular adverse events of myocardial infarction and stroke is however not anticipated to occur in pediatric patients as such events are not typically observed in pediatric populations. Nonetheless subjects will be closely monitored and those at a high risk of cardiovascular disease (eg, familial hypercholesterolemia, valvular heart disease, or Kawasaki disease) will be excluded from this study.

Events of interest specific to the pediatric patient population include cranial hyperostosis and the effect on longitudinal bone growth, as well as effects on fetal development in those female subjects with reproductive potential, and are further discussed below.

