- Adjudication of atypical femoral fractures was removed for the following reason: recent publications report that a femoral fracture is one of the most common fracture sites in children with osteogenesis imperfecta (Folkestad et al, 2017) with radiographic appearances that cannot be distinguished from atypical femoral fractures (AFF) in adults with primary osteoporosis (Nicolaou et al, Trejo et al, Vuorimies et al).
- Adjudication of potential cardiovascular events was removed. It is unexpected that a cardiovascular event will occur in this study, but if one should occur it will be thoroughly investigated. A specific adjudication process was not deemed necessary.
- Disease-related events were removed from the protocol to align with Amgen's current processes for reporting adverse events. The anticipated serious adverse event definition was removed from the protocol because all serious adverse events will be reported to health authorities in an expedited manner.
- · Clarification on analysis plan for BMD DXA
- Language in the protocol describing Self-Evident Corrections was removed from the protocol to align with Amgen's current processes
- Other changes to improve readability, correct grammar and/or remove duplicated information were made throughout the protocol.

References:

CONFIDENTIAL

Product: Romosozumab

Protocol Number: 20160227

Date: 27 April 2020

Page 3 of 43

CONFIDENTIAL

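### The search for serious cardiovascular events of interest in SAP 9.6.1 does not assure capture of stroke, one of the two events by which the protocol describes this risk

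*SAP*

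**What the plan says.** Protocol 2.3 (Pediatric Risk Assessment) says that "Key safety risks for romosozumab include serious cardiovascular events of myocardial infarction and stroke". It then applies the same pair of events to children, stating that the potential risk of serious "cardiovascular adverse events of myocardial infarction and stroke is however not anticipated to occur in pediatric patients", but that subjects will nonetheless be closely monitored. Exclusion criterion 207 lists a history of stroke by name.

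Protocol 10.4.3.7 (Adverse Events) requires tables for adverse events of interest. Its list of examples ends with "osteoarthritis, and serious cardiovascular events) will also be provided". It gives no search definition.

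SAP 9.6.1 supplies the definition: "Serious cardiovascular adverse events will be identified using cardiac and vascular system organ class (SOC) in MedDRA". The SAP's summary of changes shows that this rule came in with SAP Amendment 1. On coding, SAP 9.6.1 says only that MedDRA will be used "to code all events categorized as adverse events to a system organ class and a preferred term".

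The other categories in SAP 9.6.1 are found differently. Hypersensitivity and malignancy use narrow standardized queries. For four more, "Event of interest of hypocalcemia, injection site reaction, hyperostosis and osteoarthritis will be identified using Amgen-defined MedDRA search strategies". Osteonecrosis of the jaw is counted after adjudication.

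**The concern.** The protocol describes the risk by two clinical events, and the SAP searches for it by two organ classes. Neither class is named for the nervous system, and nothing in the rule mentions stroke. Half of the protocol's own description therefore has no stated route into the table that is meant to show it.

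The event-of-interest table is where a reader will look for this named risk. A zero there would naturally be read as no myocardial infarction and no stroke. The rule as written does not support that reading for stroke.

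Nothing at the level of this category would correct an omission. The summary of changes for Protocol Amendment 1 records that "Adjudication of potential cardiovascular events was removed", and the current Protocol 7.4.17.1 sends only potential osteonecrosis of the jaw to an adjudication committee. Membership of the cardiovascular category is decided by the search rule alone.

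**Working it through.** The documents give no figure for this point, so the check sets the texts side by side and then works through the cases that the wording leaves open.

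**Step 1. Risk against search.**

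| Item | Source | Content |
|---|---|---|
| Risk as described | Protocol 2.3 | Myocardial infarction and stroke, stated twice |
| Output required | Protocol 10.4.3.7 | Event-of-interest table for serious cardiovascular events |
| Search rule | SAP 9.6.1 | Cardiac and vascular organ classes |
| Stroke term, query or nervous-system class | SAP 9.6.1 | None named for this category |
| Primary or secondary class | SAP 9.6.1 | Not stated; coding is to one organ class and one preferred term, in the singular |
| Cardiovascular adjudication | Protocol 7.4.17.1 | None; jaw osteonecrosis only |

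**Step 2. Consistency within SAP 9.6.1.** The section introduces events of interest as found by standardized or sponsor-customized queries. Two categories use standardized queries, four use sponsor-defined searches and one uses adjudication. Serious cardiovascular events are the only category defined by whole organ classes.

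**Step 3. Would a serious stroke be captured?** The MedDRA hierarchy is not printed in either document, so where stroke terms sit is an assumption. All cases are shown.

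| Primary class of stroke terms (assumed) | Classes searched | Stroke in the event-of-interest summary? |
|---|---|---|
| Cardiac or vascular | Primary only, or primary and secondary | Yes |
| Another class | Primary only | No |
| Another class | Primary and secondary, with a secondary link to cardiac or vascular | Yes |
| Another class | Primary and secondary, with no such link | No |

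The SAP does not say which row applies. The singular wording on coding points towards a primary-class search but does not settle it.

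**Step 4. Size of the possible error.** Four cohorts of 4 give 4 × 4 = 16 subjects; six give 6 × 4 = 24. In the rows marked No, one stroke would leave the stroke contribution at 0 instead of 1/16 = 6.25% or 1/24 = 4.2% overall, and at 0 instead of 1/4 = 25% in the affected cohort.

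**Step 5. What is unaffected.** SAP 9.6.1 also tabulates all treatment-emergent, serious and fatal adverse events by organ class and preferred term, and lists every treatment-emergent event by subject. A stroke would appear in those outputs in every row above.

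**The case against.** The strongest reply has four parts.

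- **The consequence depends on a dictionary that the documents do not reproduce.** This stands. A reader might infer that the search cannot find a stroke at all. The documents do not support that, because SAP 9.6.1 does not limit the search to the primary class. They support only that capture is not assured.
- **A stroke would be seen anyway.** This also stands. A reader might infer from the removal of adjudication that nothing else would pick up the event, or that it would be lost from the report. Neither follows. Protocol 9.2.2 requires serious events to reach the sponsor within 24 hours. The medical monitor reviews data throughout, and dose level review meetings use all available adverse event data rather than this category. The Amendment 1 summary also says that any cardiovascular event would be thoroughly investigated. What remains is a possible misstatement in one summary.
- **Protocol 2.3 is background, and Protocol 10.4.3.7 says only serious cardiovascular events.** This stands in part. The operative list is not confined to two events, and a broad organ-class search is a reasonable reading for children. That is a reason to keep the organ classes. It is no reason to leave stroke to chance, since the protocol's only description of the risk names it.
- **Replacing the organ classes with narrow queries would drop other serious cardiac or vascular events.** This is correct, and it is why the remedy should add to the present rule and not replace it.

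**Conclusion.** The point holds as a gap in a safety search definition. SAP 9.6.1 fills the serious cardiovascular category only from the cardiac and vascular organ classes, and its text does not assure that stroke is included. A serious stroke would be missing from the event-of-interest summary on two assumptions: that stroke terms have their primary classification outside those classes, and that only the primary class is searched. If secondary assignments are searched, the event may already be captured.

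The size is small. The protocol does not anticipate these events in children, the planned enrolment is 16 to 24, and all analyses are descriptive. No dosing decision rests on this table, and the event would still appear in the serious adverse event tables and the subject listing. The point is nevertheless worth acting on, because the stated rule could produce a wrong zero for a risk that the protocol names as key.

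**What to change.** In SAP 9.6.1:

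1. Keep the cardiac and vascular organ classes as part of the category.
2. Add a standardized query or a preferred-term list for stroke and central nervous system vascular events, restricted to serious events.
3. State whether the organ-class search uses primary assignments only or secondary assignments as well.
4. Report myocardial infarction and stroke as separate rows within the category.

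The cost is one added search definition and two table rows. No new data, visits or protocol procedures are needed. If stroke already falls within the present search, the overall count for the category should not change on account of stroke, and the table will show explicitly that it was looked for.
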